 4. MBC (N=150)
- 8 secondary cohorts of:
 1. CRC (N=20),
 2. CRPC (N=20),
 3. ACC (N=50),
 4. Melanoma (N=50),
 5. Mesothelioma (N=50),
 6. Urothelial carcinoma (N=50; note: enrollment is being stopped [N=44] due to the opening of a urothelial efficacy expansion cohort),
 7. Ovarian cancer (N=120), and
 8. RCC, second-line, (N=20 with expansion of 60 first-line).
- 4 efficacy expansion cohorts of:
 1. Ovarian cancer, platinum refractory, prior liposomal doxorubicin (N=100);
 2. Urothelial carcinoma, platinum ineligible or progressed after at least 1 line of platinum-based therapy (N=200);
 3. Gastric and GEJ cancer, third line (N=150);
 4. HNSCC, platinum ineligible or progressed after at least 1 line of platinum-based therapy (N=150);

Subjects in the NSCLC (post platinum doublet), CRC, and CRPC cohorts will be enrolled in the USA only.

	
For subjects enrolled in the efficacy expansion cohorts and the secondary urothelial carcinoma cohort, an IERC will perform a blinded determination as to whether the criteria for tumor response or progression according to RECIST 1.1 have been met.
 
Subjects will receive avelumab intravenously as a 1-hour infusion once every 2 weeks until confirmed progression, unacceptable toxicity, or any reason for withdrawal from the trial or Investigational Medical Product (IMP) occurs. Subjects who have experienced a confirmed complete response (CR) should be treated for a maximum of 24 months after confirmation, at the discretion of the investigator. If the investigator believes that a subject may benefit from treatment beyond 24 months, it may be permissible after discussion with the sponsor. Subjects who experienced a CR and have already stopped treatment can resume treatment with avelumab at the same dose and schedule. Subjects re-initiating treatment should be assessed according to the Schedule of Assessments.
 
For subjects who achieve a CR on avelumab therapy and then subsequently develop disease progression after stopping therapy, but prior to the end of the trial, one re-initiation of treatment at the same dose and schedule is allowed at the discretion of the investigator and agreement of the trial Medical Monitor. In order to be eligible for retreatment, the subject must not have experienced any toxicity that led to treatment discontinuation of the initial avelumab therapy.
 
Prior to re-initiation of the study treatment, malignant disease needs to be radiologically re-staged to assess all known sites of the disease and to establish a new baseline for subsequent tumor measurements. Relevant safety laboratory results must be available and verified prior to re-initiating of treatment.
 
Subjects who re-initiate treatment will stay on study and will be treated and monitored according to the protocol and the “until progression” schedule in the Schedule of Assessments.

Number of Subjects
	
Expansion phase: 1610 subjects.


Trial Product
	
Avelumab will be administered as 1-hour intravenous (i.v.) infusion. Subjects will receive avelumab once every 2 weeks until confirmed progression, unacceptable toxicity, or any criterion for withdrawal from the trial or IMP occurs.
 
The dose of avelumab will be calculated based on the weight of the subject determined on the day of each drug administration.
 
Premedication with an antihistamine and with paracetamol (acetaminophen) approximately 30 to 60 minutes prior to each dose of

	
avelumab is mandatory (for example, 25-50 mg diphenhydramine and 500-650 mg paracetamol [acetaminophen] i.v. or oral equivalent). This regimen may be modified based on local treatment standards and guidelines, as appropriate.
 
Immediate access to intensive care unit or equivalent environment and appropriate medical therapy (including intravenous epinephrine, corticosteroids, antihistamines, bronchodilators, and oxygen) must be in place for use in the treatment of potential infusion reactions. Infusion of avelumab will be stopped in case of \geq Grade 2 infusion-related, allergic, or anaphylactic reactions (according to NCI-CTCAE v4.0). Following avelumab infusion, subjects must be observed for 2 hours post infusion for potential infusion-related reactions (IRRs).

Treatment and Trial Duration
	
The planned treatment duration is until unacceptable toxicity, or any criterion for withdrawal from the trial or IMP occurs.


Schedule of Visits
	
1. Screening/Baseline assessment (day -18 to first treatment)
 
2. Treatment phase
 
Visits will be conducted weekly until week 7 and every 2 weeks thereafter prior to the approval of Protocol Amendment 7. For subjects participating in the expanded PK sampling, visits at Days 2 and 3 will be required. Following the approval of Protocol Amendment 7, the visits at Week 2, 4, and 6 are no longer required and subjects will not be required to attend these visits.
 
3. Discontinuation visit and end-of-treatment visit
 
All subjects who discontinue study treatment prematurely for an AE should have a full safety evaluation at the time of discontinuation (discontinuation visit). For all subjects who have completed treatment, an end-of-treatment visit should be scheduled 4 weeks after the last administration of avelumab.
 
The end-of-treatment visit is scheduled 4 weeks after the last administration of avelumab but before any new therapy is started, if possible. The visit will comprise a full assessment of safety parameters, immunogenicity assessment, and tumor response assessment as appropriate.
 
4. Post-treatment follow-up (safety follow-up visit and survival follow-up)
 
All subjects will have a subsequent visit scheduled 10 weeks after the last administration of avelumab. The visit will include a full assessment of safety parameters.
 
AEs will be documented until the end of treatment visit. After the end of treatment visit only treatment related AEs have to be documented until the post-treatment safety follow-up visit. Subjects with a serious AE ongoing

	
at the post treatment safety follow-up must be monitored and followed up by the investigator until stabilization or until the outcome is known, unless the subject is documented as “lost to follow-up”.
 
Subjects without progressive disease (PD) at the end-of-treatment visit will be followed up for disease progression (CT / MRI scans every 12 weeks) up to 1 year. In addition, subjects will be followed for any AE suspected to be related to study treatment, especially for the occurrence of new autoimmune events up to 3 months after the last dose of avelumab.
 
After the end-of-treatment visit, subjects will be followed quarterly for survival (including assessment of any further tumor therapy). The survival follow-up will continue until 1 year after the last subject receives the last dose of avelumab.
 
Schedule of Assessments can be found in Section 12, Appendix I, of the protocol.

Randomization and Blinding	Not applicable.

CCI

CCI

CCI

8 Overview of Planned Analyses

This SAP will only address analyses for the expansion phase. Additional SAPs for Safety Monitoring Committee (SMC) analyses and for the final analysis of dose escalation phase have been developed separately. Trial endpoints specifically for dose escalation have been included into the dose escalation SAP.

The planned analyses for the expansion phase are summarized in Table 2. An additional interim analysis may be conducted 13 weeks after the start of treatment of the last subject in that cohort for selected primary and secondary expansion cohorts. Depending on subject enrollment or planning of future study, a separate primary analysis may be performed for selected secondary cohorts. Those analyses, as well as an interim safety analysis for interim CSR, are also included into Table 2.

Table 2 Planned Analyses for Expansion Cohorts

Cohort	Interim Analysis	Primary Analysis	Interim CSR and Final Analysis
NSCLC post platinum doublet	60 subjects 75 subjects all subjects	X	Pooled expansion cohorts for interim CSR and all expansion cohorts together for final analysis
NSCLC first-line	30 subjects 75 subjects all subjects	X	
MBC	75 subjects	X	
Gastric and GEJ cancer primary	75 subjects all subjects	X	
CRPC		X	
CRC		X	
2nd Ovarian cancer cohort	20 subjects 75 subjects all subjects	X	
ACC	20 subjects all subjects	X	
Melanoma	20 subjects all subjects	X	
Mesothelioma	20 subjects all subjects	X	
2nd Urothelial carcinoma cohort	20 subjects all subjects	X*	
RCC second-line	20 subjects	X	
RCC first-line	30 subjects	X	
Ovarian cancer efficacy	30 subjects 60 subjects	X	
Urothelial carcinoma efficacy	30 subjects 109 subjects*	X	
Gastric and GEJ cancer efficacy	30 subjects 90 subjects	X	
HNSCC	30 subjects 90 subjects	X	

X = Primary analysis to be conducted with a data cut-off date of the last subject first dose date + 6 months for each cohort.

* = Interim analysis will be performed after the 109th dosed subject from efficacy urothelial carcinoma cohort has reached 6 months follow-up period.

8.1 Interim Analysis

For the NSCLC (post platinum doublet and first-line), gastric/GEJ cancer, and MBC expansion cohorts, an interim analysis will be performed after the 75th subject in each cohort has reached the

time point of the second post-baseline tumor assessment scheduled in Week 13, i.e. 13 weeks after start of treatment of the 75th subject. Efficacy in this 75 subject subset of the cohort will be analyzed in terms of the unconfirmed response at Week 13. If the rate of unconfirmed response at Week 13 (according to RECIST 1.1) in the efficacy population defined as all treated subjects with measurable disease at baseline is less than 5%, enrollment in the given cohort may be stopped.

Based on a comprehensive review of the efficacy and safety data it may be considered whether recruitment in a subgroup of the study population of the given indication, defined by PD-L1 expression status, might be resumed by means of a substantial Protocol Amendment.

Statistical considerations related to this futility rule:

Under different assumptions on the true response rate in the overall population, the probabilities of observing a response rate of less than 5% in this analysis (i.e., 3 or less responders out of 75 subjects) are noted in Table 3.

Table 3 Probability of Observing a Response Rate of Less Than 5% in Interim Analysis

True response rate in overall population	Probability of 3 or less responders in 75 patients
0.03	0.81
0.05	0.48
0.10	0.05
0.15	0.002

Interim analyses on the first 75 NSCLC post platinum doublet or MBC subjects included the baseline characteristics, efficacy (excluding DR, TTR and OS), and safety evaluations. Interim analyses on the first 75 gastric/GEJ cancer or NSCLC first-line subjects will include the baseline characteristics and efficacy (excluding DR, TTR and OS).

In the NSCLC post platinum doublet cohort only, 2 additional interim analyses of efficacy parameters are planned for internal planning purposes at the following time points:

- 13 weeks after start of treatment of the 60th subject. This interim analysis was performed on demographic, disease history, and efficacy endpoints.
- 13 weeks after start of treatment of the last subject. This interim analysis will be performed on disposition, demographic and baseline characteristics, treatment exposure, and efficacy endpoints. The subgroup analyses on efficacy endpoints will be performed on all dosed subjects and on PD-L1 positive subjects based on tertiary cut-off as defined in Section 13.4.

In the first-line NSCLC primary expansion cohort, an interim analysis of response will be conducted 13 weeks after start of treatment of the 30th subject.

In the efficacy expansion cohorts, interim analyses for efficacy are planned 13 weeks after the start of treatment of the 30th subject in all cohorts, 13 weeks after start of treatment of the 60th subject in the ovarian cohort, and 13 weeks after the start of treatment of 90th subject in the gastric / GEJ

and HNSCC cohorts. The interim analyses after 60/90 subjects aim to demonstrate efficacy as specified in [Section 16.1](#). No futility rule is foreseen because the clinical activity of anti-PD-1 / anti-PD-L1 agents in these tumor types is established, and the patient populations are characterized by a high unmet medical need. If efficacy criteria are met at the interim analysis, enrollment will continue to the planned full number of subjects in order to collect further data on the primary and secondary endpoints, especially on the association between PD-L1 expression and efficacy endpoints.

In addition, in the secondary cohorts that plan to enroll more than 20 subjects, i.e., the ACC, melanoma, mesothelioma, ovarian cancer, and urothelial carcinoma cohorts, an interim analysis of response will be performed 13 weeks after the start of treatment of the 20th subject. Accrual in each cohort may be paused during the interim analysis. If no unconfirmed response according to RECIST 1.1 is observed in a given cohort in the interim analysis, accrual in that cohort will be stopped. The data included into the interim analysis are demographic, disease history, prior anti-cancer therapy, PD-L1 expression status, lesion assessment, BOR, ORR by PD-L1 expression status, and PFS overall and by PD-L1 expression status. In addition, for the ovarian cancer secondary expansion cohort, an interim analysis of response will be performed for internal planning purposes 13 weeks after the start of treatment of the 75th subject.

Enrollment of first-line RCC subjects was opened after 2 documented objective responses among the 20 subjects enrolled in the second-line RCC cohort were observed by RECIST 1.1 (2 PRs), and justified further evaluation in this patient population. In the RCC cohort, interim analyses of response will be performed 13 weeks after the start of treatment of the 20th subject of second-line RCC; and after the 30th subject of the first-line RCC.

The sequence of statistical analyses planned for urothelial cancer subjects will consider the objective to evaluate the association between tumor PD-L1 expression and BOR prospectively. In a first step, the secondary urothelial carcinoma cohort served as a “training set” for the identification of a PD-L1 expression cut-off (5%) that is most likely to identify a subset of the subject population with enhanced clinical benefit. The PD-L1 expression cut-off (5%) was specified prior to any statistical analysis of the PD-L1 expression data from the urothelial carcinoma efficacy expansion cohort (cut-off determined 11Mar2016). In the next step, the cut-off will be verified by conducting an interim evaluation with data from subjects of the efficacy expansion cohort at 6 months after the last subject’s first dose of study treatment for the 109 subjects enrolled in the urothelial carcinoma efficacy expansion cohort prior to Protocol Amendment 13. The cut-off date for this analyses was 19Mar2016. In case the cut-offs are not mutually supportive in terms of clinical efficacy endpoints, the cut-off could be refined and the remainder of approximately 100 subjects of the efficacy expansion cohort will serve as the “validation set” to qualify the tumor PD-L1 expression cut-off. Otherwise, data from subjects of the urothelial carcinoma expansion cohorts will be pooled for the final efficacy analyses of the expansion cohorts at 6 months after start of treatment of the last subject enrolled in the efficacy expansion cohort.

For each primary and secondary expansion cohort, an additional interim analysis may be conducted 13 weeks after the start of treatment of the last subject in that cohort. In general, interim

analyses at time points that are not specified in the protocol may be performed for internal planning purposes.

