8.1 Sample Size

The sample size for the dose-escalation part of the trial is not based on any statistical assumptions. Rather, it follows the “3 + 3 rule”, a well-established methodology in the design of dose-finding trials in oncology.

This trial plans for cohorts of 3 subjects to be treated at each escalating dose level. After the appearance of a single DLT, the cohort for that dose level will be expanded to 6 subjects.

Therefore, the number of subjects enrolled in the dose-escalation phase of the trial will depend on the number of dose escalation steps needed to reach the MTD. Once the dose of 10 mg/kg is

established as safe, accrual of 10 additional subjects at 3 mg/kg and 10 mg/kg each may be enrolled, for the purpose of generating additional safety, PK and receptor occupancy data, if agreed with the SMC. Once the safety of a dose of 15 mg/kg or 20 mg/kg has been established, the SMC will have the possibility to allow enrollment of up to 15 additional subjects at that dose.

Together with the 6 subjects in the once weekly 10 mg/kg cohort, the expected total sample size in the dose escalation phase of the trial will be up to 66 subjects.

The primary endpoint of the efficacy expansion cohorts is the confirmed BOR according to RECIST 1.1, as adjudicated by an IERC. The ORR will be determined as the proportion of subjects with a confirmed BOR of PR or CR. For each of these cohorts, the trial aims at demonstrating an ORR greater than 10% by means of an exact binomial test with an overall 1-sided alpha level of 0.025.

Based on an assumed ORR of 20% in an unselected population, the sample size of 150 subjects (gastric / GEJ cancer, HNSCC) will provide approximately 91% power, and the sample size of 100 subjects (ovarian cancer) will provide approximately 80% power to reject the null hypothesis of $ORR \leq 10\%$ at the primary analysis.

The sample size of 200 subjects in the urothelial carcinoma efficacy expansion cohort is expected to result in 50-60 PD-L1 positive subjects (based on an expected proportion of 85% PD-L1-evaluable subjects and a proportion of 30 to 35% PD-L1 positive subjects among those that are evaluable). Under the assumption of an ORR of 27% in PD-L1 positive subjects, the sample size of 50 to 60 PD-L1 positive subjects will provide at least 90% power to reject the null hypothesis of $ORR \leq 10\%$.

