The results of this analysis may be subject to reporting to regulatory authorities. The interim analysis is considered positive if the lower limit of the 95% CI of the confirmed BOR exceeds 10%. Results will be presented for PD-L1 positive FAS and FAS. Further details will be provided in the SAP.

The sequence of statistical analyses planned for urothelial cancer subjects will consider the objective to evaluate the association between tumor PD-L1 expression and BOR prospectively. In a first step, the secondary urothelial carcinoma cohort served as a “training set” for the identification of a PD-L1 expression cut-off that is most likely to identify a subset of the subject population with enhanced clinical benefit. The PD-L1 expression cut-off was specified prior to any statistical analysis of the PD-L1 expression data from the urothelial carcinoma efficacy expansion cohort. In the next step, the cut-off will be verified by conducting an interim evaluation with data from subjects of the efficacy expansion cohort at 6 months after the last subject’s first dose of study treatment for the 109 subjects enrolled in the urothelial carcinoma efficacy expansion cohort prior to Protocol Amendment 13. In case the cut-offs are not mutually supportive in terms of clinical efficacy endpoints the cut-off could be refined and the remainder of approximately 100 subjects of the efficacy expansion cohort will serve as the “validation set” to qualify the tumor PD-L1 expression cut-off. Otherwise, data from subjects of the urothelial carcinoma expansion cohort will be pooled for the final efficacy analyses of the expansion cohort.

For each primary and secondary expansion cohort, an additional interim analysis may be conducted 13 weeks after the start of treatment of the last subject in that cohort. In general, interim analyses at time points that are not specified in the protocol may be performed for internal planning purposes.

9 Ethical and Regulatory Aspects

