16.1 Primary Endpoint Analyses

The primary endpoint in the efficacy expansion cohorts is the confirmed BOR according to RECIST 1.1 and as adjudicated by an IERC, defined as the best response obtained among all tumor assessment visits after start of study treatment until documented disease progression (taking into account the requirement for confirmation). Only tumor assessments performed before the start of any further anti-cancer treatment will be considered in the assessment of BOR.

For the gastric / GEJ cancer, HNSCC, and ovarian cancer efficacy expansion cohorts, the primary analysis of the BOR by IERC will be conducted in the FAS, defined as all treated subjects. The number and proportion of BOR (defined as CR + PR) will be tabulated. The ORR will be determined as the proportion of subjects with a confirmed BOR of PR or CR. An exact binomial test will be performed at a 1-sided alpha level of 0.025. The primary analysis is planned 6 months after start of treatment of the last subject in the given cohort. Interim analyses will be conducted after 60% of the subjects in the given cohort have been followed up for 13 weeks. Analyses are considered positive if the lower limit of the 95% confidence interval exceed 10%. Confidence intervals will be constructed using the Clopper-Pearson method.

For the urothelial carcinoma efficacy expansion cohort, the analysis of the BOR by IERC will be conducted in the PD-L1 positive FAS followed by the FAS. The number and proportion of BOR (defined as CR + PR) will be tabulated. The ORR will be determined as the proportion of subjects with a confirmed BOR of PR or CR. An exact binomial test will be performed in the PD-L1 positive FAS and in the FAS to determine whether the null hypothesis of an $ORR \leq 10\%$ can be rejected at the 1-sided alpha level of 0.025. Interim analyses will be conducted at 4 and 6 months after the first dose date of last subject of the 109 subjects enrolled in the urothelial carcinoma efficacy expansion cohort prior to Protocol Amendment 13. Respective cut-off dates are 18Jan2016 and 19Mar2016. Analyses are considered positive if the lower limit of the 95% CI of the confirmed BOR exceeds 10%. Confidence intervals will be constructed using the Clopper-Pearson method.

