16.2 Secondary Endpoint Analyses

Clinical efficacy parameters will be analyzed descriptively in the FAS, and, in addition, for the urothelial carcinoma efficacy expansion cohort, in the PD-L1 positive FAS. Pooling of data from subjects with at least 6 months follow-up period in the urothelial carcinoma efficacy and secondary cohorts may be considered to enhance precision of estimates if data is sufficiently homogeneous. The following efficacy endpoints will be considered: The confirmed and unconfirmed BOR, per RECIST 1.1, as adjudicated by an IERC and per investigator assessment; irBOR according to modified irRC per investigator assessment, DR, TTR, and PFS time according to RECIST 1.1 criteria per IERC and investigator assessment; DR, TTR, and irPFS time according to irRC criteria

per investigator assessment; OS time. Subgroup analyses specified in Section 16.2.6 and summary of demographics will also be presented for pooled population.

The percent change in target lesions from baseline will be derived as:

- $((\text{Sum of target lesions at week XX} - \text{sum of target lesions at baseline}) / \text{sum of target lesions at baseline}) * 100\%$

The maximum reduction in target lesions from baseline will be derived across all the post-baseline assessments as:

- Minimum of $((\text{sum of target lesions at week XX} - \text{sum of target lesions at baseline}) / \text{sum of target lesions at baseline}) * 100\%$

The tumor shrinkage will be calculated based on investigator assessment for all the expansion cohorts and, in addition, based on IERC data for efficacy expansion cohorts and the urothelial carcinoma secondary cohort. The percent change from baseline in target lesions per time point as well as other relevant information will be presented in a data listing. The percent change from baseline in target lesions as well as the first occurrence of new lesion and subject off treatment overall and by PD-L1 expression status will be displayed against time point (weeks) in spider plots. The maximum reduction from baseline in the sum of target lesion diameters overall and by PD-L1 expression status will be presented per subject in waterfall plots. The PD-L1 expression status will be displayed using different colors or line styles in the plots. The time point of a tumor assessment per investigator is defined as the earliest scan date of the respective visit.

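### The SAP conflicts with itself on whether the 44-subject urothelial training cohort enters the final efficacy analysis; the test against 10% should be tied explicitly to the efficacy cohort

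*SAP*

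**What the plan says.** **Final pooling.** SAP Section 8.1 describes the secondary urothelial cohort as the training set from which the 5% PD-L1 cut-off was chosen. The first 109 efficacy-cohort subjects then verify it. If the cut-off is not supported, the remaining subjects (about 100) become a validation set. Otherwise, "data from subjects of the urothelial carcinoma expansion cohorts will be pooled for the final efficacy analyses of the expansion cohorts", timed at 6 months after the last efficacy-cohort subject starts treatment. Protocol Section 8.6 has the same sentence in the singular: "data from subjects of the urothelial carcinoma expansion cohort will be pooled for the final efficacy analyses of the expansion cohort".

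**Confirmatory test.** SAP Section 16.1 (and protocol 8.5.2.2) runs the exact binomial test for the urothelial efficacy cohort, in the PD-L1 positive FAS and then the FAS, to see whether an ORR of 10% or less "can be rejected at the 1-sided alpha level of 0.025". The decision rule is "Analyses are considered positive if the lower limit of the 95% CI of the confirmed BOR exceeds 10" percent. SAP Section 10 makes the PD-L1 positive FAS the primary population and defines it for the efficacy cohort.

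**Optional pooling.** SAP Section 16.2 says "Pooling of data from subjects with at least 6 months follow-up period in the urothelial carcinoma efficacy and secondary cohorts may be considered", provided the data are sufficiently homogeneous. Protocol 8.5.3.1 also allows pooling of secondary and efficacy cohorts and leaves the details to the SAP. Both passages concern descriptive secondary analyses.

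**What was already known.** Protocol 3.5.5.3 reports 7 responders among the 44 secondary-cohort subjects at a cut-off of 19 March 2015, in the section that justifies enlarging the efficacy cohort.

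**The concern.** The trial has two urothelial expansion cohorts, secondary (44) and efficacy (200), so the plural in SAP 8.1 most naturally means both. The sentence says the data will be pooled, at the time point that is also the efficacy cohort's primary cut-off (SAP Section 11), and it does not exclude the test against 10%. Section 16.2 makes the same pooling optional and conditional on homogeneity. SAP Section 9, which lists departures from the protocol's planned analyses, does not mention the move from one cohort to two.

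An analyst could follow 8.1 and run the final test on up to 244 subjects, or follow 10 and 16.1 and run it on 200. If the pooled version were used for the test, it would include responses known before the efficacy cohort was enlarged, and PD-L1 positive responses from the subjects used to choose the cut-off. The two versions can give different conclusions, so the choice should not be open when the results are in hand.

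**Working it through.** **Inputs from the documents.** Null ORR 10%, one-sided alpha 0.025, exact binomial, Clopper-Pearson limits (SAP 16.1). Efficacy cohort 200: "The sample size of 200 subjects in the urothelial carcinoma efficacy expansion cohort is expected to result in 50-60 PD-L1 positive subjects" (protocol 8.1). The planning proportions in that section are 85% of subjects evaluable for PD-L1 and, of those, 30 to 35% positive. Secondary cohort 44, with 7 responders (protocol 3.5.5.3).

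**Assumptions.** The documents do not give the number of PD-L1 positive training subjects. Applying the protocol's own proportions, 44 × 0.85 × 0.30 = 11.2 and 44 × 0.85 × 0.35 = 13.1, so I take 12. For new PD-L1 positive subjects I take 55, within the planned 50 to 60. The training responder count among the 12 is not given either, so I show a range.

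**1. Reproduce the plan's figure.** The protocol claims at least 90% power: "Under the assumption of an ORR of 27% in PD-L1 positive subjects", with 50 to 60 subjects. The critical count r is the smallest with P(X ≥ r | n, 0.10) ≤ 0.025; power is P(X ≥ r | n, 0.27).
- n = 50: r = 10, size 0.0245, power 90.2%.
- n = 60: r = 12, size 0.0146, power 91.8%.

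Both ends of the range reproduce, so the test has been read correctly. (Because the test is discrete, power falls below 90% at n = 51 to 54 and at 58; that is a side remark.)

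**2. FAS.**
- Efficacy cohort alone, n = 200: r = 30, P(X ≥ 30 | 200, 0.10) = 0.016.
- Pooled, n = 244: r = 35. With k responders fixed in the secondary cohort, success needs 35 − k among the 200 new subjects.

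| Secondary cohort | Needed in 200 | P(false positive) at true ORR 10% |
|---|---|---|
| 7/44 | 28 | 0.043 |
| 6/44 | 29 | 0.027 |
| 5/44 | 30 | 0.016 |
| 4/44 | 31 | 0.0095 |

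Example: 28/200 (14.0%) has a lower 95% limit of 9.5% and fails. Adding 7/44 gives 35/244 (14.3%), lower limit 10.2%, which passes.

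**3. PD-L1 positive set (55 new, 12 training).**
- Alone, n = 55: r = 11, size 0.019.
- Pooled, n = 67: r = 13. Success needs 13 − k among the 55.

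| Training responders | Needed in 55 | P(false positive) at true ORR 10% |
|---|---|---|
| 1/12 | 12 | 0.007 |
| 2/12 | 11 | 0.019 |
| 3/12 | 10 | 0.044 |
| 4/12 | 9 | 0.094 |

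**4. Cut-off selection by itself.** A simulation with a 10% ORR at every PD-L1 level chose, from 2 to 5 candidate cut-offs, the one with the highest training response rate (200,000 runs per scenario; assumed prevalences 10 to 60%; at least 3, 5 or 10 training positives required). The rejection rate for the PD-L1 positive test was 0.016 to 0.018 on the efficacy cohort alone and 0.021 to 0.0255 pooled. With the cut-off fixed in advance it stayed at about 0.017 either way.

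**The case against.** The strongest reply is that the confirmatory test is already limited to the efficacy cohort wherever it is actually specified: SAP 10 with its Table 4, SAP 16.1, and protocol 8.4 and 8.5.2.2. SAP Section 11 adds that a cohort's primary analysis uses that cohort's data, and protocol 8.5.1 that cohorts are analysed separately. The 8.1 sentence names no null value, test or alpha. This stands. A reader might infer that the SAP inflates the false-positive rate of its primary test; the documents support that only if one sentence in the interim-analysis section overrides all of these.

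A reader might also infer that the protocol rules out any pooling with the secondary cohort. It does not: protocol 8.5.3.1 allows it for descriptive use and delegates the details to the SAP. For the same reason, its absence from SAP Section 9 is not clearly an undeclared change. The singular-plural discrepancy is confined to the parallel sentences in protocol 8.6 and SAP 8.1.

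The size is also open to challenge. The 7/44 is not described as IERC-confirmed, which is what the test requires, and two fewer responders remove the effect. The PD-L1 positive counts are assumed. Selection of the cut-off, taken alone, brings the pooled test only to about its nominal level, and 5% was already the protocol's default. All of this limits the size of the concern. It does not remove the conflict between 8.1 and the sections that define the test, or the difference between mandatory pooling in 8.1 and optional pooling in 16.2.

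**Conclusion.** The point holds as a conflict within the SAP that should be settled before the final urothelial analysis; it is not a demonstrated inflation of the primary test. If 8.1 were applied to the test, the FAS false-positive probability given 7/44 would be 0.043, about 2.7 times the 0.016 of the efficacy cohort alone and above 0.025. For the PD-L1 positive set it would range from 0.007 to 0.094 over 1 to 4 training responders, against 0.019 alone.

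These are probabilities conditional on the secondary-cohort result, with a true ORR of 10% in the new subjects. That is the relevant calculation here, because the secondary-cohort data had been seen and were cited in enlarging the efficacy cohort. The figures rest on the 7/44 carrying over to the IERC-confirmed endpoint and on the assumed 55 and 12 PD-L1 positive subjects.

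**What to change.** In SAP 8.1, replace the pooling sentence with one stating that the final confirmatory ORR tests (PD-L1 positive FAS, then FAS) use the urothelial efficacy expansion cohort only, that is, the first 109 subjects plus the remainder. Add that any analysis including the secondary cohort is descriptive, under the conditions in SAP 16.2 and protocol 8.5.3.1, with no test against 10%.

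This agrees with SAP 10 and 16.1 and with protocol 8.6. Limited to the efficacy cohort, the exact false-positive rate stays at or below 0.025: 0.016 for the FAS, and 0.011 to 0.0245 for 50 to 60 PD-L1 positive subjects. The cost is a sentence or two of SAP text. No data, sample size or output is lost, since the pooled estimate and its confidence interval can still be reported.
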